8.0 Dosage Modification Based on Adverse Events (details tabulated in appendix VIII)

Strictly follow the modifications in this table for the first **two** cycles, until individual treatment tolerance can be ascertained. Thereafter, these modifications should be regarded as guidelines to produce mild-to-moderate, but not debilitating, side effects.

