8.2 Treatment schedule modifications for durvalumab

Adverse events (both non-serious and serious) associated with durvalumab exposure may represent an immunologic etiology. These adverse events may occur shortly after the first dose or several months after the last dose of treatment. Durvalumab must be withheld for drug-related toxicities and severe or life-threatening AEs per Table 8.21 below. See Section 9.0 for supportive care guidelines, including use of corticosteroids.

Table 8.21 Dose Modification Guidelines for Drug-Related Adverse Events for Durvalumab			
CTCAE System/Organ/Class	Adverse Event	Grade	Action
Gastrointestinal disorders	Diarrhea or Colitis	2	Hold all protocol treatment until Grade 0-1. If AE does not resolve to Grade 0-1 within 2 weeks, then permanently discontinue all protocol treatment
		3, 4	Permanently discontinue all protocol treatment
Investigations	Alanine aminotransferase increased, Aspartate aminotransferase increased, and blood bilirubin increased	2	Hold all protocol treatment until Grade 0-1. If AE does not resolve to Grade 0-1 within 2 weeks, then permanently discontinue all protocol treatment
		3-4	Permanently discontinue all protocol treatment
Metabolism and nutrition disorders	Glucose intolerance (Type 1 diabetes mellitus [if new onset]) or Hyperglycemia	T1DM or 2-4	Hold all protocol treatment until clinically and metabolically stable.

Table 8.21 Dose Modification Guidelines for Drug-Related Adverse Events for Durvalumab

CTCAE System/Organ/Class	Adverse Event	Grade	Action	
Endocrine disorders	Endocrine disorders-Other, specify: Hypophysitis	2-4	Hold all protocol treatment until Grade 0-1. If AE does not resolve to Grade 0-1 within 2 weeks, then permanently discontinue all protocol treatment	
	Hypothyroidism	2-4	Therapy with durvalumab can be continued while thyroid replacement therapy is instituted	
	Hyperthyroidism	2-3	Hold all protocol treatment until Grade 0-1. If AE does not resolve to Grade 0-1 within 2 weeks, then permanently discontinue all protocol treatment	
		4	Permanently discontinue all protocol treatment	
General disorders and administration site conditions	Infusion related reaction	1, 2	Follow infusion related reaction treatment guidelines (Table 9.21). Hold all protocol treatment until Grade 0-1. If AE does not resolve to Grade 0-1 within 2 weeks, then permanently discontinue all protocol treatment	

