		3, 4	Follow infusion related reaction treatment guidelines (Table 9.21). Permanently discontinue all protocol treatment	
Respiratory, thoracic and mediastinal disorders	Pneumonitis	2	Hold all protocol treatment until Grade 0-1 and corticosteroid dose is less than or equal to prednisone 10 mg per day (or equivalent). If AE does not resolve to Grade 0-1 within 2 weeks, then permanently discontinue all protocol treatment	
		3-4	Permanently discontinue all protocol treatment	
Renal and urinary disorders		2	Hold all protocol treatment until Grade 0-1 and corticosteroid dose is less than or equal to prednisone 10 mg per day (or equivalent). If AE does not resolve to Grade 0-1 within 2 weeks, then permanently discontinue all protocol treatment	
		3-4	Permanently discontinue all protocol treatment	
All Other Non-hematologic Events		3	Hold all protocol treatment until Grade 0-1 and corticosteroid dose is less than or equal to prednisone 10 mg per day (or equivalent). If AE does not resolve to Grade 0-1 within 2 weeks, then permanently discontinue all protocol treatment	
		4	Permanently discontinue all protocol treatment	

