Grade 3 diarrhea: stool frequency of ≥ 7 over baseline per day; limiting self-care ADL	Grade 3 Permanently discontinue study drug/study regimen for Grade 3 if toxicity does not improve to Grade ≤ 1 within 14 days; study drug/study regimen can be resumed after completion of steroid taper.	
 Promptly initiate empiric IV methylprednisolone 2 to 4 mg/kg/day or equivalent. Monitor stool frequency and volume and maintain hydration. Urgent GI consult and imaging and/or colonoscopy as appropriate. If still no improvement within 3 to 5 days of IV methylprednisolone 2 to 4 mg/kg/day or equivalent, promptly start further immunosuppressives (e.g., infliximab at 5 mg/kg once every 2 weeks). Caution: Ensure GI consult to rule out bowel perforation and refer to infliximab label for general guidance before using infliximab. Once the patient is improving, gradually taper steroids over ≥ 28 days and consider prophylactic antibiotics, antifungals, and anti-PJP treatment (refer to current NCCN guidelines for treatment of cancer-related infections [Category 2B recommendation]).^a
Grade 4 diarrhea: life threatening consequences	Grade 4 Permanently discontinue study drug/study regimen.	
Grade 3 colitis: severe abdominal pain, fever; ileus; peritoneal signs		
Grade 4 colitis: life-threatening consequences, urgent intervention indicated		

Hepatitis (elevated LFTs) Infliximab should not be used for management of immune-related hepatitis

Any elevation in AST, ALT or TBIL (i.e., $> \text{ULN}$)	General Guidance	
 Monitor and evaluate liver function test: AST, ALT, ALP, and TB. Evaluate for alternative etiologies (e.g., viral hepatitis, disease progression, concomitant medications).
Grade 1 AST, ALT, or TBIL AST or ALT $> \text{ULN} \times 3 \text{ ULN}$ and/or TBIL $> \text{ULN} - 1.5 \times \text{ULN}$	
 No dose modifications. If it worsens, then treat as described for elevations in the row below. 	Continue LFT monitoring per protocol.

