TBIL $>3.0 \times$ ULN	
 Hold study drug/study regimen dose until resolution to AST or ALT $\leq 3.0 \times$ ULN and/or TB $\leq 1.5 \times$ ULN, or baseline Resume study drug/study regimen if elevations downgrade to AST or ALT $\leq 3.0 \times$ ULN and/or TB $\leq 1.5 \times$ ULN, or baseline within 14 days and after completion of steroid taper. Permanently discontinue study drug/study regimen if the elevations do not downgrade to AST or ALT $\leq 3.0 \times$ ULN and/or TB $\leq 1.5 \times$ ULN or baseline within 14 days. 
For elevations in transaminases $>8 \times$ ULN or elevations in bilirubin $>5 \times$ ULN, permanently discontinue study drug/study regimen.
 
Permanently discontinue study drug/study regimen for any case meeting Hy's law criteria (AST and/or ALT $>3 \times$ ULN + bilirubin $>2 \times$ ULN without initial findings of cholestasis (i.e., elevated alkaline phosphatase) and in the absence of any alternative cause.^b Note that this does not apply to the week 2 (cycle 3) post Y90-RE when this is usually seen and subsides in the upcoming weeks (cycle 4). Also for those with Gilbert's syndrome, would need to rely on AST/ALT rather than total bilirubin.
	
 immunosuppressive therapy (i.e., mycophenolate mofetil). Discuss with study physician if mycophenolate is not available. Infliximab should NOT be used. Perform hepatology consult, abdominal workup, and imaging as appropriate. Once the patient is improving, gradually taper steroids over ≥ 28 days and consider prophylactic antibiotics, antifungals, and anti-PJP treatment (refer to current NCCN guidelines for treatment of cancer-related infections [Category 2B recommendation]).^a

Nephritis or renal dysfunction (elevated serum creatinine)

Any Grade	General Guidance	
		
 Consult with nephrologist. Monitor for signs and symptoms that may be related to changes in renal function (e.g., routine urinalysis, elevated serum BUN and creatinine, decreased creatinine clearance, electrolyte imbalance, decrease in urine output, or proteinuria). Patients should be thoroughly evaluated to rule out any alternative etiology (e.g., disease progression or infections). Steroids should be considered in the absence of clear alternative etiology even for low-grade events (Grade 2), in order to prevent potential progression to higher grade event.

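### Table 8.21 and Appendix VII conflict on whether durvalumab may resume after three toxicities, and no text clearly ranks them for cycles 3 to 5, which hold every durvalumab dose after Y90-RE

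*Combined protocol and SAP*

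**What the plan says.** Section 8.2 introduces Table 8.21 as mandatory: "Durvalumab must be withheld for drug-related toxicities and severe or life-threatening AEs per Table 8.21 below". For Grade 3 or 4 diarrhea or colitis, for Grade 3 or 4 ALT, AST or bilirubin, and for Grade 4 hyperthyroidism, the table's action is to "permanently discontinue all protocol treatment". It offers no route back.

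Appendix VII gives different dose rules for part of the same ground.

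- **Grade 3 diarrhea:** it stops durvalumab only without improvement to Grade 1 or less "within 14 days; study drug/study regimen can be resumed after completion of steroid taper".
- **Liver:** the row above its Grade 2 band holds treatment for transaminases up to 8 x ULN or bilirubin up to 5 x ULN, then says "Resume study drug/study regimen if elevations downgrade to AST or ALT" no higher than 3 x ULN and/or bilirubin no higher than 1.5 x ULN, or baseline. This must happen within 14 days, and the taper must be complete.
- **Grade 4 hyperthyroidism:** the endocrinopathy row holds until symptoms are controlled and then allows resumption. A general note also lists it among the exceptions to the Grade 4 stop.

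On force, Section 8.0 asks for strict adherence to an unnamed table in the first two cycles and then says: "Thereafter, these modifications should be regarded as guidelines to produce mild-to-moderate, but not debilitating, side effects". The 8.0 heading sends the reader to appendix VIII for details. The liver, diarrhea and endocrine tables are in Appendix VII; only the non-immune page is headed VIII.

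**The concern.** Two current texts tell the treating team opposite things about the same patient. The heading of Section 8.0 presents the appendix as the detail behind the section, and the appendix has been tailored to this trial: its liver row carries a note about week 2 (cycle 3) after Y90-RE. A clinician could reasonably act on either page.

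What is at stake is patient safety. A patient with an early Grade 3 liver event or Grade 3 diarrhea is either finished with durvalumab or re-treated a few weeks after liver irradiation. Section 1.4.5 expects liver enzymes to rise in most patients in the first 1 to 2 weeks after Y90-RE, so the liver row is the one most likely to be consulted.

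**Working it through.** The plan states no figure to reproduce. The check compares the two rule sets and then works through the dosing calendar.

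**Where the texts differ**

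| Durvalumab-related event | Table 8.21 | Appendix VII |
|---|---|---|
| Grade 3 diarrhea, Grade 1 or less within 14 days | stop | resume after taper |
| Grade 3 diarrhea, not recovered by 14 days | stop | stop |
| AST/ALT >5 to 8 x or bilirubin >3 to 5 x ULN, recovered within 14 days | stop | resume after taper |
| Same band, not recovered by 14 days | stop | stop |
| AST/ALT >8 x or bilirubin >5 x ULN | stop | stop |
| Grade 4 hyperthyroidism | stop | hold, resume after taper |
| Grade 3 pneumonitis, renal event or infusion reaction | stop | stop |

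Two readings are involved. The Appendix VII liver row has no grade label; it is taken as the start of Grade 3 because the Grade 2 row ends at 5 x ULN (AST/ALT) and 3 x ULN (bilirubin). The dose cell beside Grade 3 colitis is blank in the available text, so colitis joins the conflict only if that cell is merged with the diarrhea cell.

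**Which text ranks them**

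Cycles 1 and 2 are the doses at weeks -2 and 0. Section 8.0 makes the table strict there, and Table 8.21 is the only dose-modification table in Section 8. Doses at weeks 2, 4 and 6 fall in cycles 3, 4 and 5. There Section 8.0 relaxes the table and Section 8.2 does not.

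**Doses affected after Y90-RE**

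Inputs:
- Y90-RE is day 0, and visit windows are ±5 days (Section 4.1).
- The steroid rule is "Once the patient is improving, gradually taper steroids over" at least 28 days (Appendix VII).
- Time from onset to the start of the taper is assumed to be 0 to 5 days.
- Held doses are assumed to be skipped, because the protocol does not say whether they can be made up.

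Latest onset that still reaches a dose = last day of its window − 28 − days to improvement.

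- Week 6 (day 42 ± 5, closing on day 47): 47 − 28 − 0 = day 19; 47 − 28 − 5 = day 14.
- Week 4 (day 28 ± 5, closing on day 33): 33 − 28 − 0 = day 5; 33 − 28 − 5 = day 0.
- Resuming on day 33 leaves 47 − 33 = 14 days, so both doses can then be given.
- Week 2 (day 14 ± 5, closing on day 19): even onset on day 0 gives 0 + 28 = day 28, so this dose is lost under either text.

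By level:
- Level 1 has no dose after Y90-RE.
- Level 2 has only week 4, so it is affected only by onset up to day 0 to 5.
- Levels 3 and 4 can differ by the week-6 dose, or by weeks 4 and 6.
- Levels -1 and -2 start durvalumab at week 4 or later. The earliest event is day 23, and 23 + 28 = day 51, past the last window.

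**Sensitivity**

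- Sections 9.5.2 and 9.5.6 start the taper at Grade 1 or less. If that takes the full 14 days, the week-6 limit becomes 47 − 28 − 14 = day 5.
- Section 8.0 does not say whether its two-cycle limit follows the date of the event or of the dosing decision. Section 8.1 ties the check to each dose, which is the reading used here. On the other reading, onset on days 0 to 13 is still nominally in cycle 2, where the table is strict. Only onset from day 14 to at most day 19 would then be unranked.

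**The case against.** The strongest reply is that the plan does rank its sources. Section 8.0 is strict for cycles 1 and 2, Section 8.2 is mandatory by name, and the appendix calls itself guidelines. This stands for the first two cycles, so a reader who inferred that nothing says which text governs would go too far. It does not settle cycles 3 to 5, where 8.0 and 8.2 differ on the table's force. The appendix's recommending language heads its management column, whereas its dose column is worded as action to be taken.

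A second reply is that oversight limits the harm. There is one site, an adverse-event check before every dose, contact with the Study Chair for any DLT, and a report within one business day. Appendix VII also demands recovery and a completed taper before re-treatment. This narrows the consequence, but the overseers would be reading the same two pages.

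A third reply concerns the remedy. Making all of Table 8.21 binding throughout would also bind its Grade 2 liver row: "If AE does not resolve to Grade 0-1 within 2 weeks, then permanently discontinue all protocol treatment". Appendix VII sets no such limit at Grade 2. With enzyme rises expected soon after Y90-RE, slow-resolving Grade 2 rises judged durvalumab-related would end treatment. This objection stands and shapes the fix.

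**Conclusion.** The conflict is real and sits in current text. It covers three events: Grade 3 diarrhea improving within 14 days (colitis too, if the blank cell is merged), the liver band of AST/ALT >5 to 8 x ULN or bilirubin >3 to 5 x ULN recovering within 14 days, and Grade 4 hyperthyroidism. It is unresolved in cycles 3 to 5. Its size after Y90-RE is one dose (week 6) at levels 3 and 4 for onset by about day 14 to 19, or two doses for onset by about day 0 to 5. This assumes that held doses are skipped, that the taper starts within 5 days, and that the two-cycle limit follows the dosing decision. If held doses can be made up, later events are affected too. No frequency can be given.

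Three stronger inferences are not supported.

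- **All Grade 3-4 liver tests conflict.** They do not; above 8 x or 5 x ULN both texts stop.
- **The MTD is distorted.** Escalation counts patients with a DLT. Grade 3 colitis is always a DLT, and on the literal wording of Section 7.4.2 a related Grade 3 liver event generally is too, apart from the cycle 3/cycle 4 exception.
- **Other differences are contradictions of the same kind.** For rash, neurotoxicity, neuromotor syndromes and myositis both texts hold and allow resumption, with 2 weeks against 30 days to recover. For type 1 diabetes, Table 8.21 says "Hold all protocol treatment until clinically and metabolically stable" and Appendix VII permits treatment without interruption. These are optional harmonisation.

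**What to change.** 1. Change the Appendix VII Grade 3 diarrhea/colitis cell to permanent discontinuation. The Summary of Changes lists that same change among the FDA-requested edits, which supports this direction.
2. Align Grade 4 hyperthyroidism in Appendix VII, including the Grade 4 exception note, with Table 8.21.
3. State in Section 8.0 and at the head of Appendix VII that, for these permanent-stop events, Table 8.21 prevails in every cycle. Correct the appendix number in the 8.0 heading.
4. For the liver band, write one rule in both places. The default is Table 8.21's stop. The alternative is an explicit exception for transient rises after Y90-RE, consistent with Section 7.4.2, which does not count as a DLT a combined transaminase and bilirubin rise seen at cycle 3 that resolves at cycle 4. The FDA-requested edit does not cover this row, so the choice is the sponsor's.
5. Decide the Grade 2 liver row before making any more of Table 8.21 binding in all cycles.
6. Say whether a held dose is skipped or made up.

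The cost is a few text edits, with no new data, visits or patients. The downside is that patients with a transient Grade 3 event may lose one or two late durvalumab doses.

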Appendix VII Continued: Infusion-Related Reactions

Severity Grade of the Event (NCI CTCAE version 5.0)	Dose Modifications	Toxicity Management
Any Grade	General Guidance	
For Any Grade:
 
 – Manage per institutional standard at the discretion of investigator. – Monitor patients for signs and symptoms of infusion-related reactions (e.g., fever and/or shaking chills, flushing and/or itching, alterations in heart rate and blood pressure, dyspnea or chest discomfort, or skin rashes) and anaphylaxis (e.g., generalized urticaria, angioedema, wheezing, hypotension, or tachycardia).
Grade 1 or 2	
For Grade 1: The infusion rate of study drug/study regimen may be decreased by 50% or temporarily interrupted until resolution of the event.
 
For Grade 2: The infusion rate of study drug/study regimen may be decreased 50% or temporarily interrupted until resolution of the event. Subsequent infusions may be given at 50% of the initial infusion rate.
	
For Grade 1 or 2:
 
 – Acetaminophen and/or antihistamines may be administered per institutional standard at the discretion of the investigator. – Consider premedication per institutional standard prior to subsequent doses. – Steroids should not be used for routine premedication of Grade ≤ 2 infusion reactions.
Grade 3 or 4	
For Grade 3 or 4: Permanently discontinue study drug/study regimen.
	
For Grade 3 or 4:
 
 – Manage severe infusion-related reactions per institutional standards (e.g., IM epinephrine, followed by IV diphenhydramine and ranitidine, and IV glucocorticoid).

CTCAE Common Terminology Criteria for Adverse Events; IM intramuscular; IV intravenous; NCI National Cancer Institute.

Appendix VIII Continued: Non-Immune-Mediated Reactions

Severity Grade of the Event (NCI CTCAE version 5.0)	Dose Modifications	Toxicity Management
Any Grade	Note: Dose modifications are not required for AEs not deemed to be related to study treatment (i.e., events due to underlying disease) or for laboratory abnormalities not deemed to be clinically significant.	Treat accordingly, as per institutional standard.
Grade 1	No dose modifications.	Treat accordingly, as per institutional standard.
Grade 2	Hold study drug/study regimen until resolution to \leq Grade 1 or baseline.	Treat accordingly, as per institutional standard.
Grade 3	Hold study drug/study regimen until resolution to \leq Grade 1 or baseline. For AEs that downgrade to \leq Grade 2 within 7 days or resolve to \leq Grade 1 or baseline within 14 days, resume study drug/study regimen administration. Otherwise, discontinue study drug/study regimen.	Treat accordingly, as per institutional standard.
Grade 4	Discontinue study drug/study regimen (Note: For Grade 4 labs, decision to discontinue should be based on accompanying clinical signs/symptoms, the Investigator's clinical judgment, and consultation with the Sponsor.).	Treat accordingly, as per institutional standard.

Note: As applicable, for early phase studies, the following sentence may be added: "Any event greater than or equal to Grade 2, please discuss with Study Physician."

AE Adverse event; CTCAE Common Terminology Criteria for Adverse Events; NCI National Cancer Institute.
